1.3. Schedule of Activities

The SoA table provides an overview of the protocol visits and procedures. Refer to the STUDY ASSESSMENTS AND PROCEDURES section of the protocol for detailed information on each procedure and assessment required for compliance with the protocol.

The investigator may schedule visits (unplanned visits) in addition to those listed in the SoA table, in order to conduct evaluations or assessments required to protect the well-being of the participant.

Visit Identifier	Day -28 Screening	Day 1 Baseline	Day 15±1 Week 2	Day 29±2 Week 4	Day 57±3 Week 8	Day 85±3 Week 12 EOT	EOS, 4 weeks post EOT±3 days
	Visit 1	Visit 2	Visit 3	Visit 4	Visit 5	Visit 6	Follow-up
Informed Consent and Assent, as applicable	х						
Demographics, Medical History	Х						
Inclusion/Exclusion Criteria	Х	Х					
Physical Examination ^a	Х	Х				Х	
Vital Signs	Х	Х	Х	Х	Х	Х	Х
Height	Х						
Weight	Х	Х					
Chest X-ray	Х						
ECG	Х					Х	
Clinical Chemistry, Hematology (including coagulation panel), Lipid Profile ^b	Х			Х		Х	
HIV, HBsAg, HCV	Х						
TB test (as per site standards)	Х						
Knee MRI for adolescent participants 12 to <18 years of age ^c	Х						

Visit Identifier	Day -28 Screening	Day 1 Baseline	Day 15±1 Week 2	Day 29±2 Week 4	Day 57±3 Week 8	Day 85±3 Week 12 EOT	EOS, 4 weeks post EOT±3 days
	Visit 1	Visit 2	Visit 3	Visit 4	Visit 5	Visit 6	Follow-up
Serum Pregnancy test (for WOCBP) or FSH	х						
Urine Pregnancy test (for WOCBP only)		Х	Х	Х	X	Х	Х
IGA	Х	Х	Х	Х	Х	Х	
EASI	Х	Х	Х	Х	Х	Х	
SCORAD	Х	Х	Х	X	X	Х	
Photography for AD lesion ^d		Х				Х	X
POEM		Х	Х	X	X	Х	
ADCT		Х	Х	X	X	Х	
PP-NRS ^e	Х						
Randomization		Х					
Dispense Investigational Product		Х	Х	Х	X		
Investigational Product Administration		Х	Х	X	X	Х	
Investigational Product Accountability			Х	X	X	Х	
Contraception check ^f	Х	Х	Х	Х	X	Х	Х
C-SSRS	Х	Х	Х	X	Х	Х	Х
AEs, SAEs and Concomitant Medication Monitoring	X			·	·		X

Visit Identifier	Day -28 Screening	Day 1 Baseline	Day 15±1 Week 2	Day 29±2 Week 4	Day 57±3 Week 8	Day 85±3 Week 12	EOS, 4 weeks post EOT±3
	U U					EOT	days
	Visit 1	Visit 2	Visit 3	Visit 4	Visit 5	Visit 6	Follow-up

a. Complete physical examinations will be conducted at Screening and EOT. Brief physical examinations will be conducted at Baseline. Refer to Section 8.2.1 for details of physical examinations.

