6.1.1. Administration

Orally administered study intervention, abrocitinib 100 mg tablet(s), will be administered QD from Day 1 to Week 12. Participants will be dispensed bottles of study intervention at Day 1, Week 2, Week 4 and Week 8 visits. Study intervention administration details for substudy participants is mentioned in Section 10.10 (Appendix 10).

Participants will be given clear dosing instructions to take either 1 tablet or 2 tablets of study intervention once daily by mouth with meals, preferably in the morning whenever possible,

at approximately the same time of day. On study visit days, participants (and caregivers, if applicable) are to be instructed to refrain from dosing at home and are to administer study intervention in the clinic under observation, at the end of the study visit.

Participants will swallow the oral study intervention whole and will not manipulate or chew the medication prior to swallowing. If the participant experiences nausea, might consider administering the oral study intervention at night.

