8.3.1. Time Period and Frequency for Collecting AE and SAE Information

The time period for actively eliciting and collecting AEs and SAEs ("active collection period") for each participant begins from the time the participant provides informed consent, which is obtained before the participant's participation in the study (ie, before undergoing any study-related procedure and/or receiving study intervention), through and including a minimum of 28 calendar days, except as indicated below, after the last administration of the study intervention.

Follow-up by the investigator continues throughout and after the active collection period and until the AE or SAE or its sequelae resolve or stabilize at a level acceptable to the investigator.

For participants who are screen failures, the active collection period ends when screen failure status is determined.

If the participant withdraws from the study and also withdraws consent for the collection of future information, the active collection period ends when consent is withdrawn.

If a participant permanently discontinues or temporarily discontinues study intervention because of an AE or SAE, the AE or SAE must be recorded on the CRF and the SAE reported using the CT SAE Report Form.

Investigators are not obligated to actively seek information on AEs or SAEs after the participant has concluded study participation. However, if the investigator learns of any SAE, including a death, at any time after a participant has completed the study, and he/she considers the event to be reasonably related to the study intervention, the investigator must promptly report the SAE to Pfizer using the CT SAE Report Form.

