# 2.1.1. Primary Estimand(s)

The primary estimand is the incidence of AE/SAE regardless of whether an intercurrent event occurs. The estimand is defined according to the primary objective and is in alignment with the primary endpoint. It includes the following 4 attributes:

- Population: Patients aged 12 years and older with moderate to severe AD, as defined by the inclusion and exclusion criteria, and who are randomized;
- Variable: Binary indicator of whether any AE/SAE occurred at least once;
- Intercurrent event(s): Dosing compliance or treatment discontinuation is not considered for analysis. All data collected (including data after discontinuation of treatment) are included.
- Population-level summary: Incidence rate of AEs/SAEs, defined as the number of participants with AEs/SAEs from the time of first dose to Week 16 divided by the number of participants, in each treatment arm.

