#### PFIZER GENERAL BUSINESS

# Figure 1. Study Design (Main Study)

# **3. ENDPOINTS AND BASELINE VARIABLES: DEFINITIONS AND CONVENTIONS**

## 3.1. Primary Endpoint(s)

The primary endpoint is the incidence of AEs/SAEs, defined as the number of participants with treatment emergent adverse events, divided by the number of participants in the Safety Population (Section 4).

An adverse event will be considered treatment emergent relative to a given treatment if:

• The event starts on or after the first dose of study drug, but before the last dose plus the lag time of 28 days. The algorithm will not consider any events that started prior to the first dose date. If an AE starts on the same day as the first dose date, it will be considered treatment emergent.

or

• The event was seen prior to the start of study drug but increased in severity during the effective duration of treatment.

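### SAP 3.1 closes the treatment-emergent window one day short of the collection period, so an AE starting exactly 28 days after the last dose is collected but not counted in the primary incidence

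*SAP*

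**What the plan says.** SAP 3.1 gives the numerator of the primary endpoint as "defined as the number of participants with treatment emergent adverse events". For a new event to be treatment-emergent, the condition is: "The event starts on or after the first dose of study drug, but before the last dose plus the lag time of 28 days". That section also settles the lower boundary expressly: an onset on the date of first dose counts. It says nothing similar about the upper boundary. A second limb covers events already present before study drug that then worsen.

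The other relevant statements are these:

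- **Collection.** Protocol 8.3.1 collects AEs and SAEs from consent "through and including a minimum of 28 calendar days, except as indicated below, after the last administration of the study intervention".
- **Estimand.** SAP 2.1.1 summarises "the number of participants with AEs/SAEs from the time of first dose to Week 16 divided by the number of participants" and takes in all collected data, including data after treatment stops. SAP 6.1.1 likewise has all collected AE data analysed.
- **Dosing.** Protocol 6.1.1 says tablets "will be administered QD from Day 1 to Week 12", and that on visit days participants "administer study intervention in the clinic under observation, at the end of the study visit". The Schedule of Activities (Protocol 1.3) marks product administration at the visit headed "Day 85±3 Week 12 EOT".
- **Last visit.** The Schedule of Activities sets follow-up at "EOS, 4 weeks post EOT±3 days", with AE monitoring running through to it.
- **Declared exclusions.** SAP 6.6.1 names only pre-dose AEs as listed without being summarised.

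**The concern.** Collection includes the 28th day after the last dose, and the treatment-emergent rule excludes it. On the nominal schedule that day is the end-of-study visit, the only scheduled safety visit after treatment in the main study. A new event with onset that day would be in the database, would fall under the SAP's promise to use all collected AE data, and would still be dropped by the algorithm that builds the primary numerator. Nothing in the SAP says this is intended. AEs and SAEs are the primary endpoint, so the rule that decides which events count should agree with the collection period and the estimand.

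**Working it through.** **Inputs.** Nominal last dose: Day 85 (Schedule of Activities and Protocol 6.1.1). Lag: 28 days (SAP 3.1). End-of-study visit: 4 weeks after end of treatment, ±3 days (Schedule of Activities). Planned size: 100 per arm with a maximum margin of error of 10% (Protocol 9.5).

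**The plan's own figure.** 1.96 × √(0.5 × 0.5 / 100) = 0.098, or 9.8 points, so the stated 10% is reproduced. The point below does not depend on it; it serves only as a yardstick.

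**Day arithmetic.** The plan labels Week 8 as Day 57 and Week 12 as Day 85, so Week w is Day 7w + 1.

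- Week 12: 7 × 12 + 1 = Day 85.
- Week 16: 7 × 16 + 1 = Day 113.
- Last dose plus 28: 85 + 28 = Day 113.
- Nominal end-of-study visit: 85 + 28 = Day 113.
- Last qualifying onset day under SAP 3.1 (strictly before Day 113): Day 112.
- Last day that Protocol 8.3.1 requires to be collected (inclusive): Day 113.

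The one-day gap moves with the last dose. A last dose on Day 82 gives a window ending on Day 109, with Day 110 collected and not counted. A last dose on Day 88 gives Day 115, with Day 116 collected and not counted.

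**Does another rule rescue the event?** No. The second limb of SAP 3.1 needs an event seen before study drug, so a new onset on Day 113 fails it. Protocol 9.3.2 also refers to treatment-emergent AEs but gives no upper limit.

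**Size.** The documents give no expected AE incidence, so this is assumed. Let p be the proportion with any AE by Day 112, with constant hazard h = −ln(1 − p) / 112. The incidence added by one more day is (1 − p) × (1 − e^(−h)).

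| p by Day 112 | Added by Day 113 (percentage points) |
|---|---|
| 40% | 0.27 |
| 50% | 0.31 |
| 60% | 0.33 |
| 70% | 0.32 |

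In an arm of 100, 0.3 points is 0.3 of a participant.

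**Who is affected.** Main-study participants whose last dose is at the Week 12 visit. An adolescent dosed to about one year has a nominal last dose near Day 366, so last dose plus 28 is near Day 394 and a Day 113 event counts as treatment-emergent. The 0.3 points therefore applies to the part of each arm that stops at Week 12; over a whole arm that includes adolescents it is smaller.

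**The case against.** The strongest reply is that the mismatch is one day, in a descriptive study with no hypothesis tests or decision rules (SAP 5.1), and that 0.3 points cannot change any conclusion. That stands, and it is why the point is minor.

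A second reply is that no Week 16 visit is defined in the Schedule of Activities or the SAP visit windows, so Week 16 could mean 16 completed weeks, which is 112 days and exactly where the SAP window ends. That reading would remove the conflict with the Week 16 limit. It would not remove the conflict with Protocol 8.3.1, which includes the 28th day, or with the statements in SAP 2.1.1 and 6.1.1 that all collected data are used.

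A reader might also infer stronger versions, which the documents do not support:

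- **That the three allowed days after the nominal visit (Days 114 to 116) are wrongly lost too.** If Week 16 is Day 113, those days lie beyond the estimand on the nominal schedule. The corresponding four-day loss of about 1.1 to 1.3 points would also need every end-of-study visit to be three days late.
- **That every participant is affected.** Adolescents continuing in the substudy are not, at Day 113.
- **That onset dates cluster on the visit day and enlarge the effect.** The documents give no figure for this. The end-of-study visit has no laboratory tests or ECG, and AE onset is elicited by questioning and need not be the visit date.
- **That the window should run to the actual end-of-study visit.** That would make the counting period depend on when the visit was booked, and a late visit would carry it past Week 16.

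**Conclusion.** The rule is wrong as written, and the point is minor. For participants whose last dose is at the Week 12 visit, SAP 3.1 leaves out of the primary numerator new AEs and SAEs that start on the 28th day after the last dose, nominally Day 113. Protocol 8.3.1 collects them, and SAP 2.1.1 and 6.1.1 say collected data are included. No other section repairs this.

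The boundary conflict follows from the text and needs no assumption about event rates. Placing it on Day 113 assumes the nominal schedule. The size of about 0.3 percentage points (0.27 to 0.33) also assumes a constant hazard and 40% to 70% any-AE incidence by Day 112. It is small beside the 10-point margin.

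**What to change.** In the first limb of SAP 3.1, replace the strict upper limit with an inclusive one: the event starts on or after the first dose *and on or before the date of last dose plus 28 days*. On the nominal schedule the last counted day moves from Day 112 to Day 113, in line with Protocol 8.3.1 and with Week 16 by the plan's day numbering. Do not tie the limit to the date of the end-of-study visit.

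The cost is one phrase in the SAP and one programming condition. Data collection, visits and sample size do not change, and reported AE incidence may be very slightly higher. The change does not carry the window to Week 16 for someone who stops treatment early, whose window still closes 28 days after the last dose. That is a separate matter from this boundary.

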10.10.6. Substudy Study Treatments

There are no additional requirements for the substudy and the requirements from the main study apply, except that adolescent participants who enter the substudy will continue to receive study intervention as assigned in the main study after the 12-week treatment period, until 1 year after randomization in the main study or until they turn 18 years of age. Participants will be dispensed bottles of study intervention at Week 12, Week 24 and Week 36 visits. Please refer to the Study Intervention(s) and Concomitant Therapy section (Section 6) of the main protocol for further details.

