10.10.7.2. Substudy Early Termination/End of Treatment Visit

• A Substudy End/Early Termination Visit will be performed approximately within 1 month of the participant turning 18 years of age, OR whenever the participant discontinues from the substudy, OR 1 year after participant randomization in the main study; whichever is the sooner.

• An MRI should be arranged approximately within 1 month of the visit (but must be AFTER the participant has turned 18 years of age if participant is completing substudy due to turning 18).

- After the MRI is performed, review if any abnormal knee MRI findings then:
 - Review findings identified by central reader MRI evaluation, and (if relevant) the adjudication report, and arrange any further follow-up and investigation, if relevant and required;
 - Record medical history/adverse event/laboratory assessment abnormality as appropriate.

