10.10.8.1. Bone Safety Findings Identified in Central Evaluation of Knee MRI Images

All bone safety findings will be recorded in the CRF as either medical history or treatment emergent adverse events, as determined by the Investigator.

If any bone safety finding(s) are determined to be present in the central evaluation of the postdose knee MRI images, then the adjudication committee will adjudicate the diagnosis as per the adjudication charter.. The adjudication committee may suggest further follow up or investigation for Investigator consideration. The Investigator will receive a report of the MRI central read and the adjudication outcome, and will determine if any further follow-up or investigation is required.

The Investigator will ensure the recording of any AEs as described in the Adverse Event Reporting section (Section 8.3 and Section 10.10.9), or medical history, if relevant.

If any potential bone safety findings, as per the image review charter, are determined to be present in the MRI central read report, then these findings are to be reported to Pfizer Safety as an important medical event on the CT SAE form within 24 hours of awareness of the event. These potential bone related safety findings are to initially be detailed as potentially related to study intervention under study. If subsequently determined (e.g. following further history, examination, investigation, adjudication) that the finding is unrelated to study intervention, then this must be updated by submitting a follow up CT SAE form within 24 hours of awareness.

Incidental/Unrelated Findings:

An incidental finding is one unknown to the participant and has potential health or reproductive importance, which is discovered unexpectedly in the course of a research study, but is unrelated to the purpose and beyond the aims of the study.

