## **5. GENERAL METHODOLOGY AND CONVENTIONS**

The study will be analyzed and reported once all randomized participants have completed all scheduled procedures (or discontinued) in the main study, i.e. at study participant data set release after the completion of the main study. The substudy will be analyzed and reported after the substudy data set release following last participant last visit in the substudy. The substudy report will include analyses that are discussed in Sections 6.1 (using the SAS), 6.3, 6.5, and Appendix 2.5.

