## 6. ANALYSES AND SUMMARIES

## **6.1.** Primary Endpoint(s)

## 6.1.1. Incidence of AEs/SAEs

- Estimand strategy: Treatment policy (Section 2.1.1).
- Analysis set: Safety (Section 4).
- Analysis methodology: Descriptive statistics.
- Intercurrent events and missing data: All adverse event data collected will be analyzed regardless of dosing compliance or treatment discontinuation; missing values will not be imputed.
- The number and proportion of participants who had treatment emergent adverse events will be presented for each treatment arm. Treatment emergent adverse events will be summarized according to type, frequency, severity, seriousness and relationship to abrocitinib in each treatment arm.

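### The 28-day treatment-emergent cut-off in SAP 3.1 can leave bone findings from a permitted late knee MRI out of the substudy AE/SAE tables

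*SAP*

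**What the plan says.** **The rule.** SAP 3.1 counts a new event as treatment-emergent on this condition: "The event starts on or after the first dose of study drug, but before the last dose plus the lag time of 28 days". A second limb covers events already present before study drug that become more severe during treatment; it does not help a finding that is new.

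**Its reuse.** SAP 5 states: "The substudy report will include analyses that are discussed in Sections 6.1 (using the SAS), 6.3, 6.5, and Appendix 2.5". The table defined in SAP 6.1.1 is limited to treatment-emergent events: "The number and proportion of participants who had treatment emergent adverse events will be presented for each treatment arm". The same section also says: "All adverse event data collected will be analyzed regardless of dosing compliance or treatment discontinuation".

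**The scan.** Protocol 10.10.7.2 says: "An MRI should be arranged approximately within 1 month of the visit". Protocol 10.10.4 gives the same allowance after withdrawal during the main study period. Protocol 10.10.7.3 allows a scan before the follow-up visit if the earlier one was not done, and lets that visit move to as late as 14 days after the scan.

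**Participants turning 18.** Protocol 10.10.6 continues dosing "until 1 year after randomization in the main study or until they turn 18 years of age". Protocol 10.10.7.2 adds: "A Substudy End/Early Termination Visit will be performed approximately within 1 month of the participant turning 18 years of age". The substudy Schedule of Activities (10.10.2), however, marks study intervention administration in the combined ET/EOT column.

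**The finding.** Protocol 10.10.8.1 says: "All bone safety findings will be recorded in the CRF as either medical history or treatment emergent adverse events, as determined by the Investigator". It also requires potential bone findings in the central read to be reported on the SAE form within 24 hours of awareness, initially as potentially related to study drug.

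**The concern.** The change the substudy looks for may give no symptoms until it is imaged, so a site may well enter the scan date as the start date. Applied literally, the SAP rule then labels a finding on a scan taken 28 or more days after the last dose as not treatment-emergent, and SAP 6.1 leaves it out.

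Bone safety is the purpose of the substudy. A bone event reported to the sponsor as serious could therefore enter or leave the AE/SAE counts because of when the scanner was booked. The AE/SAE tables and the adjudicated MRI table could disagree, with nothing in the plan to explain the difference.

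**Working it through.** **The plan's own days.** EOT target: Day 1 + 365 = Day 366. Follow-up target: 366 + 28 = Day 394. Both agree with SAP Appendix 2.1.

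**Test applied.** Let *t* be the days from last dose to scan, with the scan date taken as onset. The event is treatment-emergent only if *t* < 28. One month is read as 30 days (31 in brackets).

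1. *One-year completer, last dose at the EOT visit.* *t* runs from 0 to 30 (31). Days 28 to 30 (31) fail: 3 of 31 (4 of 32) permitted days.

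2. *Same completer, scan inside the SAP's EOT MRI window, which ends at Day 380.* Visit on Day 366: *t* is at most 380 − 366 = 14, inside the rule. Visit on Day 352, the earliest allowed: 380 − 352 = 28, outside by a single day.

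3. *Early termination, with g days from last dose to the visit.* *t* runs from *g* to *g* + 30. The protocol gives no value for *g*, so a range is shown.

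| g (assumed) | t | Permitted days outside |
|---|---|---|
| 0 | 0–30 | 3 of 31 |
| 7 | 7–37 | 10 of 31 |
| 14 | 14–44 | 17 of 31 |
| 28 | 28–58 | 31 of 31 |

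The last row can occur. Protocol 7.1 requires permanent discontinuation when dosing cannot restart within 28 days of an interruption for serious infection, and lists interruptions longer than 28 days for other events. Protocol 10.10.7.4 then leads to an ET visit.

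4. *Turning 18, last dose on the birthday.* Visit delay *v* and scan delay *d* each run from 0 to 30, so *t* = *v* + *d* runs from 0 to 60 (62). Combinations with *t* ≤ 27 number 28 × 29 / 2 = 406. Those outside number 31 × 31 − 406 = 555 of 961, or 58% (32 × 32 − 406 = 618 of 1,024, or 60%).

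5. *Turning 18, dose taken at the ET visit, as the Schedule of Activities marks.* This reduces to case 1: 3 of 31.

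6. *Catch-up scan.* No upper day limit is given, because the follow-up visit may move with the scan. Only the scan-not-done case adds risk; a repeat scan for a finding already seen concerns an event already identified.

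These are counts of permitted days, not forecasts of when scans will take place.

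**Collected but not counted.** Protocol 8.3.1 sets 28 days after last dose as a minimum for AE collection, and 10.10.8.1 puts no time limit on SAE reporting of bone findings. A later finding can therefore be in the database and still be excluded from the table.

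**The case against.** - *The main bone analysis is untouched.* SAP 6.3.1 uses a treatment-policy strategy with no 28-day limit, and SAE reporting to the sponsor does not depend on the SAP. This stands. A reader might infer that the substudy's primary endpoint loses findings to this rule; the documents do not support that. (Whether a completer's scan after Day 380 maps to the EOT visit under Appendix 2.1 is a separate ambiguity.)
- *Most scans may be early.* Protocol 10.10.4 places the second MRI at the EOT visit. A reader might infer that scans typically fall 30 to 60 days after last dose; those figures are the outer edge of a range that starts at 0. This stands.
- *The 60-day case depends on one reading.* It needs the last dose at the birthday, which 10.10.6 suggests and the ET/EOT column of the Schedule of Activities contradicts. This stands. Footnote c to that schedule also gives participants who turn 18 during the main study a baseline MRI only.
- *Exclusion is not automatic.* The rule uses the start date, which neither document defines for an MRI finding. The investigator may record the finding as treatment-emergent, and SAP 6.1.1 says all collected AE data are analysed. The CRF instructions or the imaging and adjudication charters may settle the date, but they are not part of these documents. This turns certain loss into possible loss. It does not remove the gap: the SAP derives treatment emergence from dates, its table admits only treatment-emergent events, and no rule resolves the conflict.

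**Conclusion.** The point holds in a limited form. If the scan date is taken as onset, the SAP rule can exclude a reported bone AE/SAE from the substudy AE/SAE tables because of scan timing.

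The exposure is small for completers dosed at the EOT visit (days 28 to 30). It is total for early terminators whose last dose was 28 or more days before the visit. For participants turning 18 it depends on which dosing passage applies: up to about 60 days from last dose on one reading, about 30 on the other.

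It is tempting to combine these into an overall percentage of findings lost. The documents do not support one: they give no distribution of scan delays or ages, no adolescent sample size (10.10.10.1 says only who is eligible) and no expected rate of findings. The number of events affected is unknown and could be zero.

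**What to change.** 1. In SAP 3.1, with a reference from SAP 5, add for the substudy tables: *Any AE or SAE recorded from a bone safety finding on a post-dose knee MRI (ET/EOT or catch-up scan) that is new or worsened relative to the baseline MRI is counted as treatment-emergent irrespective of the 28-day lag.*
2. Add a listing that reconciles adjudicated MRI findings with AE/SAE and medical-history records. The investigator's CRF classification under Protocol 10.10.8.1 stays as it is; a finding filed as medical history then shows in the listing.
3. Reconcile Protocol 10.10.6 with the dosing mark at the ET/EOT visit in 10.10.2, so that the last-dose date is unambiguous for participants turning 18.

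A longer fixed lag would be a weaker remedy. It would have to exceed 30–31 days for completers and 60–62 days for those turning 18 on the birthday reading. It has no stated bound for early terminators, and it would bring in late events unrelated to the scan.

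The SAP changes cost one sentence and one listing on data already collected; item 3 is a protocol clarification. The downside is that the reported AE/SAE count may be slightly higher.
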